### **6.8.3      Rescue Medications and Supportive Care**

Subjects should receive appropriate supportive care measures as deemed necessary by the treating Investigator.

## 7 STOPPING RULES, DISCONTINUATION OF STUDY INTERVENTION AND SUBJECT WITHDRAWAL FROM THE STUDY

### 7.1 STUDY STOPPING RULES

Enrolment in this study will be stopped at any time for safety reasons.

The study includes DLT Stopping rules (refer to Section [6.5.1](#)). In addition, enrolment and treatment with SUPLEXA will be temporarily suspended for any of the following reasons pending review and recommendations from the DSMB:

- Any death that is not due to disease progression within 30 days after receiving SUPLEXA will result in a hold of further enrolment, until an investigation into the cause of death is performed by DSMB. If it is determined that the death was not related to the study intervention, then enrolment may restart. If the relationship between SUPLEXA infusion and death is not clear, or it appears that the death may be related to study intervention, enrolment will be held until further review. Refer to Section [8.3.7](#).
- The occurrence of two  $\geq$  Grade 4 DLTs in 2 study subjects.
- At least 3 cases of  $\geq$ Grade 3 of the following events assessed as related to study intervention:
  - Immunological related events
  - CRS
  - TLS

Suspension of the study will entail stopping the enrolment of new subjects and maintaining enroled subjects in the study. Suspension of the study will not entail cessation of dosing in subjects who did not complete the 3-dose administration unless so directed by the regulatory agencies or advised by the DSMB and agreed to by the Sponsor. The suspension will remain in effect until the case(s) and supporting information have been discussed between the Sponsor and the DSMB and the relevant regulatory agencies, if applicable, with a decision made to either resume the study or stop the study. If a decision is made to stop the study, all subjects will immediately discontinue dosing with study intervention and will undergo a follow-up visit as specified in the SoA.

The DSMB will review safety data at regular intervals, and can recommend, in its judgment, halting the study for any substantial imbalance in AEs. Sponsor additionally reserves the right to stop the study at any time for any reason. The regulatory health authorities and Australian Human Research Ethics Committee (HREC) will be notified in the event the study is stopped.

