Dose limiting toxicity (DLT) assessment			DLT assessment period						consultation with Sponsor' Medical Monitor. Cumulative dose depends on the individual subject SUPLEXA manufacturing yield in batch 1 and in batch 2.	
			1	2					Refer to Section 6.5 for DLT criteria. DLT assessment periods: Period 1: 1 week after the 1st dose (before 2 nd dose administration) Period 2: 1 week after 2nd dose (before 2nd 3rd dose administration)	

Study period	Screening		Treatment Period (Weekly dosing)			TREATMENT GAP	Treatment Extension Period	Follow Up after last dose		Notes	
			SUPLEXA Batch 1								
Study Treatment Week	-5	-5 to -1	First 3 infusions		Additional doses 		Batch 2				
Visit Window (days)			±2	±2	-1 to +7		Doses 				
AE assessment	X	X	X s		X s	X s		Every 8 weeks up to 48 weeks from last dose	EOS/ET	
s. The first 3 subjects in each cohort will be monitored closely at the clinic for at least 6 hours after each of the first 3 weekly infusion and be contacted by phone on a daily basis (weekdays) between these weekly infusions for up to 5 days post the 3rd treatment.
 
During the observation period (as specified above), all subjects will be monitored for post infusion reaction(s) and AEs every 90 minutes.
 
Subsequent subjects will be monitored for 90 min post dose for post infusion reaction(s) and AEs.
 
If any of these subjects experience an adverse event of Grade 3 or greater, the longer in-clinic monitoring window of 6 hours post each of the first 3 weekly
	

Study period	Screening		Treatment Period (Weekly dosing)			TREATMENT GAP	Treatment Extension Period	Follow Up after last dose		Notes	
			SUPLEXA Batch 1								
Study Treatment Week	-5	-5 to -1	First 3 infusions		Additional doses 		Batch 2				
			Week 0 Day 1/ Baseline	1, 2			Doses 	Every 8 weeks up to 48 weeks from last dose		EOS/ET	
Visit Window (days)		±2		±2	-1 to +7	60	-1 to +7	±5	±28		
										infusions and daily calls will be reimplemented as done for the first 3 subjects.	
										t. For subjects with unresolved treatment-related toxicity at last dosing visit, follow as medically appropriate until stabilization.	
										Only SAEs that are believed related to study intervention will be collected.	

[figure not shown]

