##### **4.1.2.2 Subsequent Weekly Infusions (SUPLEXA Batch 1 and Batch 2)**

After completion of the first 3 weekly SUPLEXA batch 1 infusions, based on emerging data from prior subjects, disease evaluation (as described below), the discretion of the Investigator, and in agreement with the subject, treating physician and the Sponsor's Medical Monitor (or designee), the treatment period of SUPLEXA may be extended as follows:

Subjects will continue to receive SUPLEXA treatments of approximately 5 B cells, every 2 weeks with a wider window -1 day to +7 days until either, a) depletion of SUPLEXA batch 1 doses \*, or b) disease progression is assessed by the Investigator per iRECIST v1.1, or c) unacceptable toxicity, or other reasons for discontinuation as described in Section 7.2.

The 5 B cells will be provided as two bags of SUPLEXA targeted at 2.5B cells until all product used, unless there is only a single dose unit left, upon which time the subject may receive a single bag until more SUPLEXA is manufactured for them.

An additional SUPLEXA batch #2 may be manufactured for a subject based on (a) last dose of batch 1 and the investigator and subject and sponsor agree, then prior to the administration of the last SUPLEXA dose, blood can be drawn for SUPLEXA manufacturing of batch 2; or (b) > 2 weeks and < 8 weeks after the last dose of SUPLEXA administered, blood is collected for batch 2.

Note that subjects enroled in SUPLEXA-101, Version 3.0 or 2.0, and had SUPLEXA manufacturing started on or before October 31, 2022, may logistically be unable to have the consecutive administration of the recommended dosing regimen. These patients are therefore exempt from the defined gap in dosing, and the sequential dosing regimen described above. However, upon possible restarting additional doses of SUPLEXA, the dosing must be sequential until either, a) depletion of SUPLEXA batch 1 doses \*, or b) disease progression is assessed by the Investigator per iRECIST v1.1, or c) unacceptable toxicity, or other reasons for discontinuation as described in Section 7.2.

Subjects will be monitored at the clinic for at least 90 minutes (+/- 30 min) after each infusion for AE and ISR.

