To account for the well-recognized phenomenon of tumor pseudo-progression or delayed response with immunotherapies, subjects may continue to receive SUPLEXA beyond RECIST v1.1 defined progression at the discretion of the Investigator. To confirm disease progression according to iRECIST, pseudo-progression will be further assessed at the next tumor assessment imaging time point after 4 weeks later but not exceeding 8 weeks from the date of initial documentation of suspected disease progression, and provided no other drug related adverse event occur warranting immediate cessation for clinical reasons. Otherwise, patients will continue to be dosed until all doses are used or progression is confirmed, whichever comes first.

\*For each subject treatment duration will be variable and will depend on SUPLEXA manufacturing yield. It is anticipated that batch 1 (manufactured during screening) may be sufficient for up to 15 individual 2.5M SUPLEXA doses. In this regimen that would mean 3 doses as once a week dose, thereafter 3 doses at 2-week intervals, and one dose at the two-week interval to exhaust all product made. When batch 1 is depleted, batch 2 will be prepared (as described above during screening). During batch 2 manufacturing period, there may be a gap of up to 60 days in dosing.

Decision for treatment extension will be based on:

- Subject's overall safety status including AE rate, clinically significant findings from safety laboratory (including parameters indicative of TLS, e.g., uric acid elevation), physical examination, vital signs; or

- Subject deriving clinical benefit from treatment with SUPLEXA based on RECIST v1.1 and iRECIST for solid tumours and laboratory parameters for haematological malignancies; Subjects who are already enroled and received at least 3 weekly doses, treatment extension will be based on their latest radiographic scan / laboratory evaluation; or
- Exploratory outcomes (pharmacodynamics and correlative biomarkers), if available for review.

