#### **4.3 DOSE JUSTIFICATION FOR SUPLEXA THERAPEUTIC CELL DOSE**

The initial cumulative dose selected for this study was based entirely on preclinical mouse xenograft studies in which we dosed mice at ~28x the intended human regimen 3 clinical doses with an option to extend to 6 doses, with each dose approximately 2.5 B cells (range 1.9-3.9 B cells). Given the complete absence of treatment related adverse events for SUPLEXA in the ongoing human study, we propose that after the first 3 doses, administration of up to 14 additional treatments of 5B cells every 2 weeks will be well tolerated, and the actual number of doses depends on the SUPLEXA manufacturing yields for each of 2 patient-specific SUPLEXA batches.

The DSMB will provide an additional review of all safety data and predetermined points in the progress of the clinical study.

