## 6.5 DOSE LIMITING TOXICITY CRITERIA

A DLT is defined as the occurrence or start of any of the events listed below during the treatment of the first 3 subjects in each cohort that are assessed as related to study intervention (SUPLEXA) by the Investigator or the Sponsor. An AE should not be considered as a DLT if it can reasonably be attributed to underlying disease, disease progression, concomitant medications, or other extraneous causes. Worsening of pre-existing medical illness could be due to study intervention and should not be excluded from consideration as a DLT.

The first 15 subjects will be assessed for DLT. For each subject, the DLT assessment period will comprise of 2 parts as follows (Refer to [Figure 5](#)):

- The first DLT assessment period – 1 week after the first dose (prior to administration of the second dose).
- The second DLT assessment period - 1 week after the second dose (prior to the administration of the 3rd dose)

Subjects who withdraw before the end of the DLT assessment period for reasons other than DLTs will be replaced.

All toxicities will be graded by the local site Investigator using National Cancer Institute (NCI) common terminology criteria for adverse events (CTCAE) v5.0.

The following will be considered DLTs:

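### The only suspension count in Section 7.1 set at Grade 4 uses DLTs, which are assessed before dose 3, so it does not count related Grade 4 events on the 5-billion-cell infusions

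*Combined protocol and SAP*

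**What the plan says.** Section 7.1 (Study Stopping Rules) gives three triggers for temporary suspension pending DSMB review:

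- a death within 30 days of SUPLEXA that is not due to progression;
- two DLTs of at least that severity: "Grade 4 DLTs in 2 study subjects";
- at least three related events of Grade 3 or higher that are immunological, CRS or TLS.

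Only the second is set at Grade 4, and it counts DLTs. Section 6.5 fixes when DLTs are assessed. The last window is described thus: "The second DLT assessment period - 1 week after the second dose", closing before dose 3. The Schedule of Activities agrees: "Period 2: 1 week after 2nd dose".

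The documents are less settled on who is assessed. Section 6.5 says "The first 15 subjects will be assessed for DLT", but its definition of a DLT refers to events "during the treatment of the first 3 subjects in each cohort". Section 6.5.1 applies its individual dosing rules to every subject, and the DLT row of the Schedule of Activities has no 15-subject limit.

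The higher dose starts after the first three weekly infusions. Section 4.1.2.2: "Subjects will continue to receive SUPLEXA treatments of approximately 5 B cells, every 2 weeks". Section 4.3 foresees up to 14 such treatments.

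**The concern.** Safety is the primary objective. Section 4.3 supports the 5-billion-cell infusions by the absence of treatment-related adverse events in the ongoing study, whose regimen was about 2.5 billion cells per dose. The amount given in one infusion therefore doubles on evidence from the lower amount, and the one count set at Grade 4 is tied to windows that have closed before the doubling.

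The suspension rule adds to this. Under Section 7.1 a suspension stops new enrolment but does not by itself stop dosing in subjects who have yet to complete the first three doses. The dosing it would pause is thus mainly dosing after dose 3, where this bullet counts nothing. Two subjects could have, say, related Grade 4 hepatic and cardiac events on 5-billion-cell infusions without meeting any numeric trigger for a study-level pause.

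**Working it through.** **1. Reproduce the plan's figure of 14 additional treatments (Section 4.3).**
Inputs: up to 15 dose units per batch (Section 4.1.2.2), two batches, three single-unit weekly doses, then two units per infusion. The unit is taken as 2.5 billion cells, as in the rest of the protocol; Section 4.1.2.2 prints it with an M at this point.

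- Batch 1: 15 − 3 = 12 units, giving 6 double infusions.
- Batch 2: 15 units, giving 7 double infusions and 1 single, so 8 infusions.
- Additional infusions: 6 + 8 = 14, which matches Section 4.3.
- Total: 3 + 14 = 17 infusions and 30 × 2.5 = 75 billion cells.

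**2. Share of dosing followed by a DLT window.** The windows follow doses 1 and 2, which is 2 × 2.5 = 5 billion cells.

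| Course | Infusions followed | Cells followed |
|---|---|---|
| Minimum, 3 doses | 2 of 3 (67%) | 5 of 7.5 billion (67%) |
| Batch 1 only, 15 units | 2 of 9 (22%) | 5 of 37.5 billion (13%) |
| Both batches, 15 units each | 2 of 17 (12%) | 5 of 75 billion (6.7%) |

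In every row, the number of 5-billion-cell infusions followed is zero.

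**3. Does another reading of DLT close the gap?** The definition sentence in Section 6.5, read alone, has no end date. It would then reach 3 subjects × 2 cohorts = 6 of about 60. The rules in Section 6.5.1 apply to each subject, but they use the same two windows and end when dose 3 is given. Neither reading gives a count for subjects in general at 5 billion cells.

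**4. What Section 7.1 counts at 5 billion cells.**

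| Related event on a 5-billion-cell infusion | Numeric trigger |
|---|---|
| Fatal within 30 days, not progression | Yes, one death |
| Grade 3 or higher CRS, TLS or immunological | Yes, at the third case |
| First two Grade 4 CRS, TLS or immunological cases | None |
| Other non-fatal Grade 4 (e.g. cytopenia, hepatic, cardiac) | None |

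Section 7.2.1 mentions effects on normal tissues but does not define an immunological event. A broad reading could move some organ toxicity from the last row to the three-case rule.

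**5. How often would a count at any dose cause a pause?** The documents give no Grade 4 rate, so the per-subject rate p is assumed. With X ~ Binomial(n, p), P(X ≥ 2) = 1 − (1 − p)^n − n·p·(1 − p)^(n−1).

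| p | n = 30 | n = 60 |
|---|---|---|
| 1% | 4% | 12% |
| 2% | 12% | 34% |
| 5% | 45% | 81% |
| 10% | 82% | 99% |

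Example, n = 30 and p = 1%: 1 − 0.740 − 0.224 = 0.036. The two low rates show the cost in pauses that may prove unneeded; the two high rates show how often a real problem would prompt review.

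**The case against.** The strongest reply is that the 5-billion-cell infusions are well guarded already. The three-case rule has no dose window and covers CRS and TLS, which lead the list of potential risks in Table 1. Section 7.2 permanently stops any subject with a related life-threatening Grade 4 event. Life-threatening events are SAEs, reported within 24 hours. Extension beyond dose 3 needs the Medical Monitor's agreement, and its listed grounds begin with "Subject's overall safety status including AE rate". The DSMB and the sponsor can halt the study at their discretion, and Section 4.3 adds: "The DSMB will provide an additional review of all safety data and predetermined points". Finally, 5 billion cells every two weeks is the same average weekly amount as 2.5 billion every week.

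All of this stands, and it shows that isolated related Grade 4 events would not go unseen. It does not supply a study-level count for the two uncovered rows above: the individual rule stops the subject, not the study, and the review provisions state no number. The weekly average is unchanged, but the amount in a single infusion doubles.

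Three stronger readings are tempting and are not supported.

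- A reader might infer that nothing numeric operates at 5 billion cells. The death trigger and the three-case rule both do.
- A reader might infer that the Grade 4 bullet is already used up, because Section 2.3.1 reports more than 15 treated subjects. Section 6.5 names the first 15, but Section 6.5.1 and the Schedule of Activities carry no such limit, so it is unclear whether DLT assessment has ended.
- A reader might compare pause probabilities under a two-subject Grade 4 count and the three-case rule. The latter also counts Grade 3, and the documents give no rates for either grade, so using one rate for both would understate the existing rule.

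**Conclusion.** The point holds as a specific gap. Section 7.1's one count set at Grade 4 does not reach the 5-billion-cell infusions. Related, non-fatal Grade 4 toxicity there that is not CRS, TLS or immunological meets no numeric suspension trigger, and the first two Grade 4 CRS, TLS or immunological cases do not meet one either.

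The size depends on how long a subject is treated. One of three infusions lies outside the DLT windows at the minimum course, and 15 of 17 with two full batches. Extension is optional and depends on yield, so the second figure is an upper bound.

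The conclusion rests on reading DLT as Section 6.5 and the Schedule of Activities define its assessment periods. It also assumes that no count is set elsewhere. The DSMB charter was not available and may contain one; if so, the remaining task is to align Section 7.1 with it. This is worth changing because the study's main safety question after dose 3 concerns the doubled infusion. It does not show that subjects at that dose are unprotected.

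**What to change.** Replace the DLT bullet in Section 7.1 with: *Related events of Grade 4 or higher that meet the toxicity criteria listed in Section 6.5, in 2 subjects, counting any subject and any dose from first dose to 30 days after last dose; after DSMB clearance the count restarts.* Keep the other triggers and the discretionary powers.

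Retaining the Section 6.5 criteria matters. They require, for example, that Grade 4 neutropenia lasts at least 7 days, and they restrict which laboratory values count. Without them, transient laboratory findings could pause the study. The restart prevents the condition from staying met after the DSMB has cleared the events.

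The cost is one bullet and a matching line in the DSMB charter. Section 8.3.1 already has adverse events collected until 30 days after the last dose or the start of new anticancer therapy, whichever is first, and SAEs for the full 30 days, with related SAEs after that. The downside is the occasional temporary pause that proves unneeded, at the frequencies shown for assumed rates of 1% and 2%. Subjects still in their first three doses would continue dosing during a pause unless regulators direct otherwise, or the DSMB advises otherwise and the sponsor agrees.

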### 7.2 DISCONTINUATION OF STUDY INTERVENTION

In some instances, it may be necessary for a subject to permanently discontinue study intervention. Please also refer to stopping rules described in Section [7.1](#).

A subject must permanently discontinue study intervention if they meet one of the following individual stopping rules:

- Any Grade 4 life threatening events assessed as related to study intervention.
- $\geq$ Grade 3 immunological-related event assessed as related to study intervention (refer to Section [7.2.1](#))

A subject may also discontinue study intervention for reasons including but not limited to:

- Adverse event
- Lost to follow-up
- Non-compliance with study drug
- Physician decision
- Pregnancy (refer to Section [7.2.2](#))
- Progressive disease
- Protocol deviation
- Study terminated by Sponsor
- Withdrawal by subject
- Death

Permanent discontinuation of study intervention does not mean withdrawal from the study, and the subject will be encouraged to remain in the study, complete the ET visit and then continue to complete all study visits as per the SoA, including all follow-up visits.

For subjects who have discontinued study intervention due to reasons other than disease progression, tumour assessment will be continued at the protocol-specified schedule until documented disease progression or initiation of subsequent anticancer therapy or until 24 months after the last dose of study intervention.

The primary reason for discontinuation from study intervention should be documented on the appropriate eCRF.

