### Non-haematologic:

1.  $\geq$  Grade 3 non-haematologic toxicity, except for the following Grade 3 events that are considered either not an adverse event or events that could be managed with standard of care:
  - a) Grade 3 inflammatory reaction attributed to a local anti-tumour response (e.g., inflammatory reaction such as pain, irritation, or localized rash at sites of metastatic disease, lymph nodes, etc.).
  - b) Grade 3 fatigue lasting  $\leq 3$  days.
  - c) Grade 3 diarrhea, nausea, or vomiting lasting  $\leq 3$  days without or with use of anti-emetics or anti-diarrheals per standard of care.
  - d) Grade 3 rash and/or pruritis without use of corticosteroids or anti-inflammatory agents per standard of care.

2. Any Grade 3 or Grade 4 non-haematologic laboratory value if:
  - a) Clinically significant medical intervention is required to treat the subject and does not resolve within 72 hours, or
  - b) Potential drug-induced liver toxicities with laboratory parameters as described below
    - $\geq$  Grade 3 and above elevation in ALT or AST if an alternative explanation other than the study intervention is not available.
    - $\geq$  Grade 3 and above elevation of total bilirubin of any duration if an alternative explanation other than the study intervention is not available.
    - Grade 2 elevation AST/ALT with concurrent elevation of total bilirubin  $>2 \times$ ULN or INR  $>1.5 \times$ ULN if an alternative explanation other than the study intervention is not available.

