#### **6.5.1 Dose Modifications and Individual Stopping Rules due to DLT**

All eligible subjects are planned to receive a minimal cumulative dose of approximately 7.5 billion cells of SUPLEXA administered as target of 2.5 billion cells per individual SUPLEXA doses. The first 3 doses will be administered at least 1 week apart (unless delayed due to DLTs as described below) at Day 1 (baseline), Week 1 and Week 2.

During the study, the cumulative dose of study intervention will not be modified unless triggered by rules governing DLT (as described below); that is, subjects experiencing a DLT which does not resolve within 3 weeks or 2 DLTs may only receive 1 or 2 infusions, each 2.5 billion cells (for these subjects, cumulative dose may range between 2.5 billion cells to 5.0 billion cells).

[figure not shown]
The DSMB will convene to review all available data collected during the DLT assessment period(s) including Investigator's impressions and provide an additional layer of oversight. The DSMB will make recommendations to the Sponsor on enrolment modifications.

The rules below will apply independently to the solid tumours and haematologic malignancies in parallel and for each subject in the study.

1. Enrol a subject and administer 1st dose on Day 1. Assess for DLTs during the first DLT assessment period (1 week post 1st infusion).
  - a) No DLT, continue to 2nd dose at Week 1 (Day 8) – refer to item 2 below,
  - b) Subject experienced a DLT (per DLT criteria in Section 6.5) and the event resolved within 3 weeks to baseline levels (Grade 1 or lower)?
    - i) Yes, continue to 2nd dose – refer to item 2 below
    - ii) No, permanently discontinue study intervention and subject will continue to be followed-up as part of the study (unless withdraw consent and start other anti-cancer therapies) as described in Section 7.2.
2. Administer 2nd dose. Assess for DLTs during the 2nd DLT assessment period (1 week post 2nd infusion)
  - a) No DLT, continue to 3rd dose – refer to item 3 below

- b) Subject experienced a DLT (per DLT criteria in Section 6.5)
  - i) If first occurrence of DLT and the event resolved within 3 weeks to baseline levels (Grade 1 or lower)?
    - Yes, continue to 3rd dose – refer to item 3 below

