### **7.2.1      Immunological effects: Action and Follow-Up Assessment**

SUPLEXA impact on normal tissues is a theoretical concern but one which was not observed in nonclinical studies conducted in the organoid PDX or xenograft or PDX animal models. A subject experiencing an immunological event of CTCAE Grade 3 or greater will permanently discontinue study intervention.

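### The DLT steps in Section 6.5.1 permit a further dose after events for which Section 7.2 requires permanent discontinuation

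*Combined protocol and SAP*

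**What the plan says.** Section 6.5.1 sets out what happens after each of the first two doses. If a first DLT occurs, items 1b and 2b(i) ask one question, whether "the event resolved within 3 weeks to baseline levels (Grade 1 or lower"). If yes, the next dose is given. If no, study intervention stops permanently. A second DLT also stops it. The same section states that "the cumulative dose of study intervention will not be modified unless triggered by rules governing DLT".

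Section 7.2 lists events after which a subject must stop permanently. The first is "Any Grade 4 life threatening events assessed as related to study intervention". The second is a related immunological event of Grade 3 or higher, and Section 7.2.1 repeats that rule: "A subject experiencing an immunological event of CTCAE Grade 3 or greater will permanently discontinue study intervention". Neither section makes an exception for an event that resolves.

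Section 6.5 defines DLTs as related events and describes their scope in two ways: events occurring "during the treatment of the first 3 subjects in each cohort", and then "The first 15 subjects will be assessed for DLT". Non-haematologic toxicity of Grade 3 or higher counts as a DLT, "except for the following Grade 3 events" that Section 6.5 goes on to list.

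**The concern.** The two sections give opposite instructions for the same subject. Take cytokine release syndrome needing ventilator support, which Appendix 7 (Section 10.7) classes as Grade 4 and life-threatening. Suppose it is judged related, starts in the week after dose 1 and resolves to Grade 1 within 3 weeks. Section 6.5.1 item 1b(i) then leads to dose 2, while Section 7.2 rules out any further dose.

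This is a first-in-human study, and the error would be re-exposure after a life-threatening related event. The reporting consequence is smaller: adverse events leading to discontinuation, part of the primary endpoint, would depend on which section a site followed. The DLT count itself would not change.

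**Working it through.** There is no planned figure to reproduce. The check compares the texts and then counts who could still be affected.

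**Where the rules overlap**

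- *Relatedness.* Section 6.5 requires it for every DLT, and both Section 7.2 rules require it too. Every DLT therefore passes that part of Section 7.2.
- *Grade 4 life-threatening events.* The Grade 3 exemptions in Section 6.5 do not reach Grade 4, so a related life-threatening non-haematologic toxicity is a DLT. If it resolves in time, Section 6.5.1 continues and Section 7.2 stops.
- *Immunological events of Grade 3 or higher.* Unless it is one of the exempt Grade 3 events, such an event is a DLT, and the same conflict arises.
- *Outside the overlap.* Grade 4 laboratory values that are not life-threatening do not meet the wording of Section 7.2. The exempt Grade 3 events are not DLTs, so they do not reach items 1b(i) and 2b(i).

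**Whether any text sets precedence**

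Section 6.5.1 cites Section 7.2 only on branches that already discontinue, and not as a check before re-dosing. Its cumulative-dose sentence names the DLT rules alone. It then identifies the subjects who may receive only 1 or 2 infusions as those with an unresolved DLT or two DLTs; subjects who meet Section 7.2 are not mentioned.

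**Whether another rule would catch the case**

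For a single surviving subject, the Section 7.1 suspension needs Grade 4 or higher DLTs in 2 subjects, or 3 related cases of Grade 3 or higher immunological events, cytokine release syndrome or tumour lysis syndrome. Even then, "Suspension of the study will not entail cessation of dosing in subjects who did not complete the 3-dose administration", unless regulators direct it or the data safety monitoring board (DSMB) advises it and the sponsor agrees. Both DLT windows fall before dose 3. Discussion with the sponsor (Section 8), investigator judgement (Section 10.3.3) and DSMB review (Section 6.5.1) are discretionary for that subject.

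**Who could still be affected**

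Section 2.3.1 reports that by 19 September 2022 more than 15 subjects, so at least 16, had received 3 to 6 doses with no related adverse event reported. All were past both DLT windows.

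- If DLT assessment covers the first 15 subjects: max(0, 15 − 16) = 0 remain.
- If it covers the first 3 in each of the 2 cohorts: with a and b subjects dosed and a + b ≥ 16, the number remaining is max(0, 3 − a) + max(0, 3 − b). This is 0 if both cohorts have at least 3, and 3 only if one cohort has none. Section 2.3.1 gives no split, so the range is 0 to 3.

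The statement in Section 6.5.1 that its rules apply to every subject does not widen the DLT definition in Section 6.5, so later subjects are not counted.

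The chance of at least one qualifying event among n subjects is 1 − (1 − p)^n. The documents give no value of p, so these rates are assumptions, with n = 3:

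- p = 1%: 1 − 0.99³ = 3.0%
- p = 2%: 1 − 0.98³ = 5.9%
- p = 5%: 1 − 0.95³ = 14.3%

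These are ceilings on a conflict. The event must also be a first DLT, start within a week of dose 1 or 2, and resolve within 3 weeks.

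**The case against.** The best reply is that the rules add to each other. Section 7.2 says must, without exception, and refers to Section 7.1, which cites Section 6.5.1. On this reading, passing the DLT check does not cancel a separate mandatory stop. The cumulative-dose sentence also cannot be taken literally, because it would then override discontinuation for pregnancy or withdrawal, which nobody intends. This reading is plausible and probably what the sponsor means. It is nowhere stated, however, and Section 6.5.1 tells the site to continue on exactly the branch where the stop is needed.

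A second reply is that a life-threatening event is a serious adverse event and must reach the sponsor within 24 hours (Section 8.3.1), with causality already assessed (Section 10.3.3). The sponsor would therefore normally know before the next dose. That stands as mitigation for the Grade 4 limb, but it is a duty to notify and does not bar re-dosing. It is also weaker for Grade 3 immunological events, which are not always serious.

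A third is that few or no subjects remain. The Section 1.1 synopsis already describes DLT evaluation in the past tense. This also stands, and it limits the size of the problem without removing the contradiction.

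**Conclusion.** The concern holds. Followed literally, Section 6.5.1 items 1b(i) and 2b(i) lead to re-dosing of subjects whom Sections 7.2 and 7.2.1 require to stop, and no visible text resolves the conflict. The overlap is narrow and the expected frequency low: 0 to 3 remaining subjects, with a chance of a qualifying event of at most 3.0% to 14.3% under the assumed rates of 1% to 5%.

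This rests on Section 6.5 limiting DLT assessment to the early subjects, on the dosing status reported in Section 2.3.1, and on Figure 5, which is not shown, containing no exception of its own. The point should be fixed because the potential harm is serious and the correction is simple, even though it may never be triggered.

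**What to change.** In Section 6.5.1, add to items 1b(i) and 2b(i): unless the event meets a mandatory discontinuation criterion in Section 7.2, in which case study intervention is permanently discontinued even if the event resolves. Add Section 7.2 to the cumulative-dose sentence as a further reason for a reduced dose. Make the same change in Figure 5 if it shows these branches.

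The cost is one clause in two items, one cross-reference and possibly a figure edit, with ethics committee approval of the amendment as Section 10.1.1.4 requires. A subject whose event has resolved loses further doses, but Section 7.2 already requires that.
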